**Unique Protocol ID: TAUgcMRTbooster**

**November 1st 2021**

## **Statistical Analysis Plan**

### **Between-group differences at baseline**

To verify there is no difference between the two groups in baseline characteristics such as age, years of education, dwell time on threat, or social anxiety symptoms, independent-samples t-test will be conducted. To verify there is no difference in gender distribution between groups, a Chi-square test will be conducted.

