### **Replication of GC-MRT efficacy**

To confirm that target engagement will have occurred (i.e., dwell time on threat will have decreased from pre- to post-treatment), two 2-way Analyses of Variance (ANOVAs) will be conducted on the percentage of dwell-time on threats with time as a within-subject factor (ANOVA 1: pre- or post-treatment measurement, ANOVA 2: Session 1, 2, 3, or 4) and group (experimental or control) as a between-subject factor.

To examine whether social anxiety symptoms will have decreased from pre- to post-treatment, a 2-way ANOVA will be conducted on the Leibowitz Social Anxiety Scale (LSAS) scores with time (pre- or post-treatment) as a within-subject factor and group (experimental or control) as a between-subject factor.

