### **The effect of active booster vs. control booster on stress levels during the speech task**

To examine whether reported stress levels will have changed differently in the experimental group compared to the control group throughout different phases of the speech task, a 2-way ANOVA will be conducted on the Visual Analogue Scale - Anxiety (VAS-A) scores with group (experimental or control) as a between-subject factor (experimental, control), and the measurement time as a within-subject factor (1 - baseline, 2 - after task introduction, 3 - after listening to the musical track, 4 - after preparation to the speech and before the speech begins, 5 - after the speech task is over).

Specifically, we hypothesize that the difference between the groups according to which the experimental group will report lower state anxiety levels compared to the control group will emerge between time points 3 and 4 and will sustain until time point 5. To confirm this hypothesis, simple effect analyses will be conducted on the difference between the groups in time points 3, 4, and 5. It is expected that simple effects for time points 4 and 5 will be significant, and the results of these contrasts are hereby declared as a-priori expected regardless of the significance of the above-described omnibus ANOVA.

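### Non-significant baseline tests cannot verify that the groups are alike, and the VAS-A simple effects and PSPS t-tests use no baseline covariate

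*SAP*

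**What the plan says.** The SAP section *Between-group differences at baseline* gives the purpose of its tests as "To verify there is no difference between the two groups in baseline characteristics". The continuous variables are "such as age, years of education, dwell time on threat, or social anxiety symptoms, independent-samples t-test will be conducted". For gender it says: "To verify there is no difference in gender distribution between groups, a Chi-square test will be conducted". The section sets no equivalence margin and attaches no action to any result.

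In *Replication of GC-MRT efficacy*, dwell time is analysed by two time-by-group ANOVAs ("ANOVA 1: pre- or post-treatment measurement, ANOVA 2: Session 1, 2, 3, or 4"). LSAS is analysed by one ANOVA on "scores with time (pre- or post-treatment) as a within-subject factor and group (experimental or control) as a between-subject factor".

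In the section on stress levels during the speech task, VAS-A is analysed by a group-by-time ANOVA over five ratings, beginning "1 - baseline, 2 - after task introduction, 3 - after listening to the musical track". The specific hypothesis is tested separately: "simple effect analyses will be conducted on the difference between the groups in time points 3, 4, and 5". The contrasts expected to be significant, at times 4 and 5, are declared "a-priori expected regardless of the significance of the above-described omnibus ANOVA".

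The section on performance quality compares the judges' PSPS scores by independent-samples t-tests. No model anywhere in the SAP names a baseline covariate.

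**The concern.** There are two separate points.

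The first is inference. A significance test can give evidence against equality; failing to reject is not evidence for it. A test whose stated job is to confirm that the groups are alike cannot do that job, and in small groups it would pass sizeable imbalances. A report that follows the plan would call the groups comparable without support.

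The second is the use of baseline information. Pre-treatment LSAS and the time 1 VAS-A rating will already have been collected. Neither is used in the VAS-A simple effects or the PSPS t-tests. A chance imbalance in a prognostic variable is therefore left in those contrasts, and they are less precise than they could be at almost no cost.

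**Working it through.** The SAP states no sample size, alpha, SD or correlation, so there is no figure of its own to reproduce. All sizes below rest on assumptions: two-sided alpha 0.05; n = 20, 30 or 40 per arm; correlation r between covariate and outcome of 0.3, 0.5 or 0.7.

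**1. What a baseline t-test would let through.** The largest observed standardised difference that is still non-significant is t(0.975, 2n−2) × √(2/n). Power to flag a true difference comes from the noncentral t distribution.

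| n per arm | t × √(2/n) | Largest non-significant difference | Power, true 0.3 SD | Power, true 0.5 SD |
|---|---|---|---|---|
| 20 | 2.024 × 0.316 | 0.64 SD | 15% | 34% |
| 30 | 2.002 × 0.258 | 0.52 SD | 21% | 48% |
| 40 | 1.991 × 0.224 | 0.45 SD | 26% | 60% |

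**2. Where baseline enters each analysis.**

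| Analysis | Role of baseline |
|---|---|
| Dwell time, pre/post ANOVA | Repeated level; the interaction is a change-score comparison |
| Dwell time, sessions 1 to 4 ANOVA | Pre-treatment value not included |
| LSAS, pre/post ANOVA | Repeated level; the interaction is a change-score comparison |
| VAS-A, five-time ANOVA | Time 1 is a repeated level |
| VAS-A simple effects, times 3, 4 and 5 | None stated |
| PSPS t-tests | None |

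A simple effect of group at time 4 compares the groups' time 4 means. Having time 1 as another level of the same ANOVA does not adjust that comparison.

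**3. What a covariate would change.** Relative to the unadjusted contrast, the ANCOVA variance is about 1 − r², before the small loss of degrees of freedom. An observed imbalance D in the covariate shifts the unadjusted contrast by about r × D. Take D = 0.4 SD, which is non-significant at all three sample sizes.

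| r | Variance ratio 1 − r² | Shift r × 0.4 |
|---|---|---|
| 0.3 | 0.91 | 0.12 SD |
| 0.5 | 0.75 | 0.20 SD |
| 0.7 | 0.51 | 0.28 SD |

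**4. Conditional error rate.** Suppose there is no true booster effect, D = 0.4 SD and r = 0.5. The unadjusted contrast then has mean 0.20 SD and standard error √(2/n) × √0.75, and is judged against ±1.96 × √(2/n). By normal approximation, the chance of a significant result is about 6%, 9% and 11% at 20, 30 and 40 per arm, against a nominal 5%. Under random allocation, an observed imbalance of 0.4 SD or more on a given variable has probability of about 21%, 13% and 8% at those sizes.

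**The case against.** Four objections deserve weight.

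- **Baseline is not ignored.** A reader might infer that no analysis uses baseline values. The documents do not support that: pre-treatment dwell time, pre-treatment LSAS and time 1 VAS-A are repeated levels in time-by-group ANOVAs. This stands, and it confines the gap chiefly to the VAS-A simple effects and the PSPS t-tests.
- **The baseline tests decide nothing.** One might add that five tests at 0.05 carry a 1 − 0.95⁵ = 23% chance of at least one spurious difference. That figure needs independent tests, which the SAP does not establish; its list of variables is open-ended, and all are measured on the same people. No planned analysis depends on the results, so a false alarm has no stated consequence. This stands, and the figure forms no part of the point.
- **The comparisons are not invalid.** A reader might infer that unadjusted VAS-A and PSPS comparisons are biased. If allocation was random, they are unbiased over allocations and their standard errors already allow for chance imbalance. The SAP does not describe allocation; the protocol may. What remains is lost precision and error conditional on the imbalance that occurs.
- **The sizes are assumed.** A 0.5 SD imbalance would pass at 20 or 30 per arm but would be flagged at 40, where the limit is 0.45 SD. No single imbalance should be quoted as if it passed at every sample size.

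The choice of covariate is also partly judgement: time 2 is the last VAS-A rating before the musical track and could be argued for in place of time 1. That is a reason to name one in advance, not to name none.

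**Conclusion.** The point holds in a limited form. The verification purpose cannot be met by non-significant tests at any sample size, and that follows from the SAP's wording alone. The limits of 0.64, 0.52 and 0.45 SD illustrate it under assumed alpha 0.05 and 20, 30 and 40 per arm.

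The missing adjustment is a shortfall in efficiency and robustness. At an assumed correlation of 0.5 the contrast variance would fall to about 0.75 of its unadjusted value; the gain is small at 0.3 and large at 0.7. It matters most for the VAS-A simple effects, because they test the specific hypothesis and do not depend on the omnibus result.

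The change should be made, but its absence would not invalidate the trial's comparisons under random allocation.

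**What to change.** 1. In *Between-group differences at baseline*, remove the significance tests and the aim of verifying equality. Report means and SDs by group (counts for gender) with standardised differences.
2. For the VAS-A contrasts at times 3, 4 and 5, pre-specify ANCOVA with the time 1 VAS-A rating and pre-treatment LSAS as covariates.
3. For the PSPS scores, pre-specify ANCOVA with pre-treatment LSAS as covariate.
4. State that the covariates are used whatever imbalance is observed, so that the decision to adjust cannot follow from the baseline data.

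The cost is a few lines of SAP text, two error degrees of freedom for each VAS-A contrast and one for each PSPS comparison. At 20 per arm the VAS-A contrasts would go from 38 to 36. No new data are needed.

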### **Replication of GC-MRT efficacy**

To confirm that target engagement will have occurred (i.e., dwell time on threat will have decreased from pre- to post-treatment), two 2-way Analyses of Variance (ANOVAs) will be conducted on the percentage of dwell-time on threats with time as a within-subject factor (ANOVA 1: pre- or post-treatment measurement, ANOVA 2: Session 1, 2, 3, or 4) and group (experimental or control) as a between-subject factor.

To examine whether social anxiety symptoms will have decreased from pre- to post-treatment, a 2-way ANOVA will be conducted on the Leibowitz Social Anxiety Scale (LSAS) scores with time (pre- or post-treatment) as a within-subject factor and group (experimental or control) as a between-subject factor.

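### The planned repeated-measures ANOVAs drop anyone lacking one measurement from that ANOVA; mixed models on all observed data would answer the same questions without that loss

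*SAP*

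**What the plan says.** The SAP section 'Replication of GC-MRT efficacy' sets out two ANOVAs on the percentage of dwell time, each with group between subjects and time within subjects: "ANOVA 1: pre- or post-treatment measurement, ANOVA 2: Session 1, 2, 3, or 4". For LSAS it sets out one more, with "time (pre- or post-treatment) as a within-subject factor".

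In the section on stress levels during the speech task, "a 2-way ANOVA will be conducted on the Visual Analogue Scale - Anxiety (VAS-A) scores", with group between subjects and five ratings within subjects. Rating 4 comes after preparation and before the speech. The last is "5 - after the speech task is over". The same section adds that "simple effect analyses will be conducted on the difference between the groups in time points 3, 4, and 5", and declares the contrasts at times 4 and 5 as expected in advance, whatever the overall ANOVA shows.

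The SAP names no analysis set, no imputation, no mixed model and no sensitivity analysis for any of these outcomes. It does not say whether the simple effects use the participants in the ANOVA or all ratings available at each time.

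**The concern.** The within-subject factors have 2, 4 and 5 levels. A classical mixed-design ANOVA needs every level for each person and otherwise excludes that person listwise. So this concerns the method the SAP names, and not only what it leaves unsaid about missing data.

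The loss applies to each ANOVA separately:

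- A missed session removes a person from the four-session dwell-time ANOVA.
- A missing post-treatment value removes a person from the pre/post dwell-time ANOVA, the LSAS ANOVA, or both.
- A missing post-speech rating removes a person from the VAS-A ANOVA, together with the four ratings that were obtained.

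The VAS-A case matters most. If some participants lack rating 5, their rating 4 is also lost from the overall ANOVA, and from the time 4 simple effect if that is run on the same sample. Time 4 is one of the two points on which the SAP rests its hypothesis. If the hypothesis is true, controls are more anxious at time 4. Loss driven by anxiety would then fall more heavily on controls and shrink the contrast.

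**Working it through.** The SAP gives no sample size, SD, effect size, correlation or missing-data rate, so there is no planned figure to reproduce. Everything below is illustration under stated assumptions. Only the numbers of levels (2, 4 and 5) come from the SAP.

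**1. Participants lost from an ANOVA.** If each of k measurements is independently missing with probability p, the share lost is 1 − (1 − p)^k.

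| ANOVA | k | p = 5% | p = 10% |
|---|---|---|---|
| Pre/post (LSAS, dwell time) | 2 | 1 − 0.95² = 9.8% | 1 − 0.90² = 19.0% |
| Four sessions (dwell time) | 4 | 1 − 0.95⁴ = 18.5% | 1 − 0.90⁴ = 34.4% |

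These are upper illustrations. Missed sessions tend to fall on the same people, and clustered missingness removes fewer of them. If only the last measurement can be missing, the loss is simply p: 5% or 10%. That is the relevant case for VAS-A when the gap is at rating 5.

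**2. Effect on the time 4 contrast when rows are complete-case.** Assumptions: VAS-A at time 4 is normal with SD 1; the true group difference is 0.60 SD; the log-odds of lacking rating 5 rise by 1 or 1.5 per SD of time 4 anxiety, by the same rule in both groups; overall loss is 5%, 10% or 20%. The estimate is the difference in mean rating 4 among those who have rating 5.

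| Overall loss | Slope 1: control / experimental loss | Estimate | Slope 1.5: control / experimental loss | Estimate |
|---|---|---|---|---|
| 5% | 6.3% / 3.7% | 0.58 | 6.8% / 3.2% | 0.56 |
| 10% | 12.4% / 7.6% | 0.56 | 13.2% / 6.8% | 0.53 |
| 20% | 24.1% / 15.9% | 0.53 | 25.3% / 14.7% | 0.49 |

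The bias runs from 0.60 − 0.58 = 0.02 SD to 0.60 − 0.49 = 0.11 SD, always toward zero. In this setting every rating 4 was observed, so an analysis that uses them all has no such bias at time 4.

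**3. A harsher mechanism, and what a valid analysis recovers.** Assumptions: a true difference of −0.50 SD at times 4 and 5; correlation 0.5 or 0.7 between ratings; rating 5 lost whenever rating 4 exceeds a fixed threshold. The threshold is set so that 5%, 10% or 20% of controls lose rating 5, which gives about 1.6%, 4% and 9% in the experimental group.

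- Time 4, complete rows: about −0.43, −0.39 and −0.33.
- Time 5, complete rows: −0.47, −0.44 and −0.42 at correlation 0.5; −0.45, −0.43 and −0.38 at correlation 0.7.
- Time 5, estimated from all observed ratings by a method valid under missing at random: about −0.50 in every case.

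**4. Missing completely at random.** With 10% loss unrelated to anxiety, the complete-row estimates stay at about −0.50. Only the standard error grows, by 1/√(1 − 0.10) = 1.05.

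**The case against.** The strongest reply is that the SAP never says completers only. The restriction is inferred from the method, and a protocol that is not shown may hold an imputation rule under which the ANOVAs could run with nobody removed. This stands as a limit on certainty. It does not remove the point, because the SAP fixes the estimator and neither states nor refers to anything that would change how it treats incomplete rows.

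Several stronger readings are tempting and are not supported:

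- **That one gap removes a person from the trial.** It removes them from one ANOVA. The t-tests on speech performance, for example, do not depend on VAS-A ratings.
- **That the time 4 rating is always discarded.** This holds for the overall ANOVA. For the simple effects the SAP does not name the sample. A group comparison at time 4 using all available ratings would avoid the time 4 bias shown above. At time 5 it would still be restricted to those who have that rating.
- **That participants will skip rating 5 because they are anxious.** The SAP does not say what happens to someone who declines or stops the speech, or whether they are still rated. The loss rates and slopes above are assumptions.
- **That the independence formula can be applied to all five VAS-A ratings.** The ratings appear to be phases of a single speech task. If the gap is at rating 5, the loss is the share lacking that rating and nothing larger.

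It is also fair to say that the illustrated bias is modest, that it is absent under missing completely at random, and that none has been quantified for LSAS or dwell time.

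**Conclusion.** The point holds in a limited form. As specified, each within-subject ANOVA loses every participant who lacks one of its measurements, and the SAP adds nothing to prevent this. The certain cost is wasted data wherever measurements are missing. Bias is possible, not shown: it requires missingness related to anxiety.

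For the time 4 VAS-A contrast on complete rows, an assumed 5-20% loss of rating 5 with a slope of 1-1.5 per SD turns a true 0.60 SD into about 0.58-0.49 SD. For the four-session dwell-time ANOVA, 19% or 34% of participants lost is an upper figure, under independent missingness of 5% or 10% per session. A mixed model gives the same group-by-time effects when data are complete, so the change is a cheap improvement that should be made. It does not correct an analysis shown to be invalid.

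**What to change.** For VAS-A, LSAS and dwell time, replace the repeated-measures ANOVAs with linear mixed models fitted by REML with an unstructured covariance and fixed effects of group, time and group-by-time, using every observed measurement. Take the group contrasts at times 3, 4 and 5 from the VAS-A model, which also settles which participants those contrasts use. Keep the complete-case ANOVAs as a sensitivity analysis, and report missing values by group and time so that readers can judge how much the choice matters.

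The cost is revised SAP wording and slightly more analysis work, with no new data. The mixed models rely on missing at random. If loss depends on values never observed, they can be biased too.

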### **The effect of active booster vs. control booster on stress levels during the speech task**

To examine whether reported stress levels will have changed differently in the experimental group compared to the control group throughout different phases of the speech task, a 2-way ANOVA will be conducted on the Visual Analogue Scale - Anxiety (VAS-A) scores with group (experimental or control) as a between-subject factor (experimental, control), and the measurement time as a within-subject factor (1 - baseline, 2 - after task introduction, 3 - after listening to the musical track, 4 - after preparation to the speech and before the speech begins, 5 - after the speech task is over).

Specifically, we hypothesize that the difference between the groups according to which the experimental group will report lower state anxiety levels compared to the control group will emerge between time points 3 and 4 and will sustain until time point 5. To confirm this hypothesis, simple effect analyses will be conducted on the difference between the groups in time points 3, 4, and 5. It is expected that simple effects for time points 4 and 5 will be significant, and the results of these contrasts are hereby declared as a-priori expected regardless of the significance of the above-described omnibus ANOVA.

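### The claim that the VAS-A group difference emerges between time points 3 and 4 has no test of change over that interval, and time point 3 has no stated role

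*SAP*

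**What the plan says.** The section on the effect of the booster on stress levels plans that "a 2-way ANOVA will be conducted on the Visual Analogue Scale - Anxiety (VAS-A) scores", with two groups and five measurement times. T3 follows the musical track, T4 follows preparation and precedes the speech, and T5 follows the speech. The stated purpose is to see whether stress "changed differently in the experimental group compared to the control group throughout different phases of the speech task".

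A specific hypothesis follows: the lower anxiety in the experimental group "will emerge between time points 3 and 4 and will sustain until time point 5". The confirming analysis is that "simple effect analyses will be conducted on the difference between the groups in time points 3, 4, and 5". The expected outcome is given for two of the three points: "It is expected that simple effects for time points 4 and 5 will be significant". These contrasts are declared a priori "regardless of the significance of the above-described omnibus ANOVA".

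No contrast compares the group difference at T4 with the group difference at T3. No result is specified for T3.

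**The concern.** Emergence between T3 and T4 is a statement about change. With D3 and D4 as the group differences at T3 and T4, it says that D4 is larger than D3 in favour of the experimental group. The planned tests ask whether D3, D4 and D5 each differ from zero. A significant D4 beside a non-significant D3 does not show that D4 and D3 differ, and a significant D4 beside a significant D3 has no interpretation in the plan.

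T3 comes directly after the musical track, so a difference already present at T3 is a case that the analysis should be able to separate from one that appears during preparation. As written, a report could follow the plan exactly and state that the difference emerged between T3 and T4 when it did not change over that interval.

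**Working it through.** **Hypothesis and test side by side**

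| Statement | Quantity needed | What the SAP tests |
|---|---|---|
| Groups differ at T4 and at T5 | D4, D5 | Simple effects at T4 and T5 (adequate) |
| Difference emerges between T3 and T4 | D4 − D3 | Nothing specific |
| Difference is sustained to T5, relative to T3 | D5 − D3 | Nothing specific |
| Any non-parallel course over five times | Group-by-time interaction, 4 df | Omnibus ANOVA, not a condition for the planned contrasts |

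**Inputs.** The SAP gives no sample size, SD, correlation or effect size, so there is no planned figure to reproduce. All of the following are assumptions: n = 20/30/40 per group; SD 1 at each time; equal correlation r = 0.6 between times (0.5 to 0.7 as a range); a group difference of 0.5 SD where present; two-sided 0.05 tests. T4 and T5 are counted only in the expected direction. Simulation used 20,000 trials per setting.

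**Case A: the difference is constant from T3 on** (0, 0, 0.5, 0.5, 0.5), so D4 − D3 = 0 and nothing emerges.

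| n per group | 20 | 30 | 40 |
|---|---|---|---|
| T4 and T5 both significant | 20% | 32% | 45% |
| of these, T3 also significant | 70% | 77% | 83% |
| T4 and T5 significant, T3 not | 5.9% | 7.2% | 7.6% |
| Omnibus interaction significant | 56% | 76% | 88% |
| Interaction, T4 and T5 all significant | 13% | 27% | 41% |

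The T4−T3 contrast is significant in about 5% two-sided, or about 2.5% in the expected direction. Over r = 0.5 to 0.7 the first row spans 18 to 48% and the third 5.0 to 8.8%. The interaction does not protect the timing claim here, because it responds to the change between T2 and T3.

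**Case B: no difference at any time.** T4 and T5 are both significant in the expected direction in 0.4 to 1.0% of trials. The simple effects are sound for the question they address.

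**Case C: the difference first appears at T4** (0, 0, 0, 0.5, 0.5). The SD of an individual's change is √(2(1 − r)) = √0.8 = 0.894, so the standardised contrast is 0.5/0.894 = 0.559. The noncentrality is 0.559 × √(n/2) = 1.77/2.17/2.50, against 0.5 × √(n/2) = 1.58/1.94/2.24 for the T4 simple effect.

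| n per group | 20 | 30 | 40 |
|---|---|---|---|
| Power, T4−T3 contrast | 0.41 | 0.57 | 0.69 |
| Power, T4 simple effect | 0.34 | 0.48 | 0.60 |
| Both contrasts (T4−T3, T5−T3) | 0.24 | 0.40 | 0.55 |
| Both simple effects (T4, T5) | 0.21 | 0.33 | 0.45 |

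Under these assumptions, the test that matches the hypothesis has somewhat more power than the tests named in the plan.

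**The case against.** Four points can be made for the plan.

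- **T3 has an implied role.** Three points are tested and significance is expected at only two, so T3 is naturally read as the point where no difference is expected. On that reading the 20/32/45% is too harsh: a significant T3 would visibly contradict the timing claim, and the relevant figure is about 6 to 8%. This largely stands as to size. It does not turn the pattern into a test of change, its rate is still above the 2.5% of the contrast, and the requirement is not written down.
- **Independence from the omnibus test is ordinary for planned contrasts.** This stands, and it is not a fault in itself. The interaction does address whether stress "changed differently in the experimental group compared to the control group throughout different phases of the speech task". What it lacks is any restriction to the interval that the hypothesis names.
- **The consequence is narrow.** This stands. The group comparisons at T4 and T5 are unaffected.
- **The contrast can be weak.** This stands too. With r = 0.4 its power is 0.29/0.41/0.52 against 0.34/0.48/0.60 for the T4 simple effect. If 0.25 SD is already present at T3 and 0.5 SD at T4 (r = 0.6), its power is 0.14/0.19/0.23, and both contrasts succeed together in only about 5/8/11%. Low power in that second case reflects a smaller true change over the interval. It is a reason to keep the simple effects, not a reason to let them carry the timing claim.

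**Conclusion.** The concern holds and should be fixed. The SAP states a hypothesis about change between two time points and names tests that do not measure that change, with no rule for T3. This follows from the text and rests on no assumed figure.

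The size does rest on assumptions. With a constant 0.5 SD difference from T3 on, 20 to 40 per group and r between 0.5 and 0.7, the stated expectation for T4 and T5 is met in 18 to 48% of trials in which nothing emerged. It is met in 5.0 to 8.8% if a non-significant T3 is also required. The second range is the fairer measure for a reader who takes that requirement as implied. What is at stake is when the difference arose, not whether the groups differ at T4 and T5.

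**What to change.** In the section on stress levels during the speech task:

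1. Pre-specify the group-by-time contrast T4−T3, the between-group difference in change from T3 to T4, as the test of emergence, and T5−T3 as the test that it is sustained.
2. Keep the simple effects at T4 and T5 as planned tests of a group difference at those points, and report them with T3, each with a 95% CI.
3. State the role of T3, and that a non-significant T3 will not be read as absence of a difference.
4. Say which result supports which statement: the contrasts for timing, the simple effects for a difference at T4 and T5. Conflicting results then have a defined reading.

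The cost is SAP wording only: the data and model are the same and no planned test is removed. The sponsor should accept that the contrast is less precise than the T4 comparison if the T3–T4 correlation is below 0.5, and that it has low power if part of the effect is already present at T3.

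### The a priori anxiety contrasts at time points 4 and 5 compare raw group means and do not adjust for each participant's own earlier ratings: a possible gain in precision, uncertain at time point 5.

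*SAP*

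**What the plan says.** The SAP section on stress levels plans this omnibus model: "a 2-way ANOVA will be conducted on the Visual Analogue Scale - Anxiety (VAS-A) scores with group (experimental or control) as a between-subject factor". The five ratings form "1 - baseline, 2 - after task introduction, 3 - after listening to the musical track", followed by a rating just before the speech (4) and one after it (5).

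The hypothesis is that the group difference "will emerge between time points 3 and 4 and will sustain until time point 5". It is to be confirmed as follows: "simple effect analyses will be conducted on the difference between the groups in time points 3, 4, and 5". For time points 4 and 5, "the results of these contrasts are hereby declared as a-priori expected regardless of the significance of the above-described omnibus ANOVA".

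Time points 1 and 2 enter only as levels of the time factor. The section on between-group differences at baseline tests "baseline characteristics such as age, years of education, dwell time on threat, or social anxiety symptoms" but adjusts no later analysis for any of them, and VAS-A is not among its named examples. No other section of the SAP supplies an adjustment.

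**The concern.** The contrasts at time points 4 and 5 carry the claim about the booster's effect on stress. A simple effect of group at one time point estimates the raw difference in means at that time. People differ stably in the state anxiety they report, and those differences stay in the error term. Two ratings on the same scale, from the same participants and before the musical track, could remove part of that variation.

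What is at stake is power and the width of the confidence interval. Bias and type I error are not at issue if allocation was random, which the SAP does not state. Using time points 1 and 2 as levels of the omnibus ANOVA is not an error.

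**Working it through.** **Inputs.** The SAP gives no sample size, SD, effect size, alpha or correlation, so there is no planned figure to reproduce. Assumed: two equal groups of n = 30 (also 20 and 50), standardised difference d = 0.5, two-sided alpha 0.05, unit variance at every time point. Two correlation patterns are used: equal correlation r between all ratings, and AR(1), where correlation decays as rho to the power of the number of steps apart.

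**Variance of the adjusted contrast relative to the raw one**, with k covariates explaining a share R² of the outcome variance within groups:

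ratio = (1 − R²) × (2n − 3)/(2n − 3 − k)

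The second factor is the cost of estimating the slopes. For n = 30 and k = 2 it is 57/55 = 1.036.

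**R² from time points 1 and 2 together:**
- equal correlation: R² = 2r²/(1 + r); for r = 0.5, 0.5/1.5 = 0.333
- AR(1): R² = rho⁴ at time point 4 (two steps from time point 2) and rho⁶ at time point 5 (three steps)

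**Power** comes from the noncentral t with 2n − 2 − k degrees of freedom and noncentrality d/√((2/n) × ratio). Raw power at n = 30 is 0.478.

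Equal correlation, n = 30 (same result at time points 4 and 5):

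| r | R² | variance ratio | change in SE | power |
|---|---|---|---|---|
| 0 | 0 | 1.036 | +1.8% | 0.464 |
| 0.1 | 0.018 | 1.018 | +0.9% | 0.471 |
| 0.2 | 0.067 | 0.967 | −1.6% | 0.490 |
| 0.3 | 0.138 | 0.893 | −5.5% | 0.522 |
| 0.5 | 0.333 | 0.691 | −17% | 0.629 |
| 0.7 | 0.576 | 0.439 | −34% | 0.819 |

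AR(1), n = 30:

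| rho | power, time 4 | power, time 5 |
|---|---|---|
| 0.4 | 0.474 | 0.466 |
| 0.5 | 0.488 | 0.470 |
| 0.6 | 0.518 | 0.482 |
| 0.7 | 0.573 | 0.512 |
| 0.8 | 0.682 | 0.586 |

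Over this AR(1) range the SE changes by +0.5% to −22% at time point 4 and by +1.6% to −13% at time point 5.

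**Break-even.** The ratio falls below 1 when R² exceeds k/(2n − 3): 2/57 = 0.035 at n = 30, 2/37 = 0.054 at n = 20, 2/97 = 0.021 at n = 50. At n = 30 this means r above 0.14 under equal correlation. Under AR(1) it means rho above 0.035^(1/4) = 0.43 at time point 4 and above 0.035^(1/6) = 0.57 at time point 5.

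**Other sizes**, equal correlation 0 to 0.7: at 20 per group, raw 0.34 and adjusted 0.32 to 0.63; at 50 per group, raw 0.70 and adjusted 0.69 to 0.96.

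**Simulation check.** Simulated trials (40,000 per setting at n = 30) compared a raw t-test with ANCOVA and agreed with the formula to within 0.01. Type I error was 4.7% to 5.3% throughout, raw and adjusted.

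**Which covariates.** In the simulation at time point 4 with r = 0.7, time point 2 alone gave 0.749 and both ratings 0.818, a gain of 7 points. Under AR(1) with rho = 0.8 the figures were 0.689 and 0.681, a cost of under 1 point. A plain change score is not an equal substitute: its variance ratio is 2(1 − r), which exceeds 1 whenever r is below 0.5 (1.4 at r = 0.3).

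**The case against.** The strongest reply is that nothing here is wrong. A prespecified raw contrast is valid under random allocation, and the proposed gain rests wholly on assumed correlations. At time point 5, half of the a priori claim, AR(1) correlation up to 0.6 gives a small loss or no visible gain. That stands, and is why the point is put as a possible improvement.

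Second, the group-by-time interaction already removes stable differences between people. That is true of the omnibus test, but the a priori contrasts stand regardless of it and gain nothing from it.

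Third, simple effects after a mixed ANOVA may use a pooled error term rather than a separate t-test, and the SAP does not say which. Pooling changes the error estimate and degrees of freedom, not the estimated difference. With 30 per group it puts raw power at 0.483 to 0.488, so the loss at zero correlation becomes 0.488 − 0.464 = 2.4 points instead of about 1.5. The gain at correlations of 0.5 or more remains.

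Fourth, adjustment is safe only if the groups had not diverged by time point 2. The expected timing of the effect supports this, but it is a hypothesis and not a description of treatment. The section on replication of GC-MRT efficacy also uses the same group factor over the treatment sessions ("ANOVA 2: Session 1, 2, 3, or 4) and group (experimental or control) as a between-subject factor"). This condition has to be settled from the protocol before the covariates are adopted.

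**Conclusion.** The concern holds as an efficiency point of moderate weight: the change should be made, but the present analysis is not invalid. At the assumed 30 per group and d = 0.5, the trade is a loss of about 1.5 points of power at worst (2.4 against a pooled error term), against gains of about 15 points at an equal correlation of 0.5 and 34 at 0.7. Under AR(1) of 0.8 the gain is about 20 points at time point 4 and 11 at time point 5. Adjustment pays once the two ratings together explain more than about 3.5% of the outcome variance, which is less certain at time point 5. The conclusion assumes random allocation and no group-specific treatment before time point 2; the SAP alone settles neither. Confidence is medium.

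**What to change.** First confirm against the protocol that the groups were treated alike up to time point 2. Do not use as a covariate any rating taken after group-specific treatment began.

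If that is confirmed, keep the five-level group-by-time ANOVA as the omnibus description and add, before group-level VAS-A data are seen:

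> The group differences in VAS-A at time points 4 and 5 (confirmatory) and at time point 3 will be estimated by ANCOVA at each time point, with VAS-A at time points 1 and 2 as covariates. A missing covariate value will be replaced by the mean of that rating over both groups. Unadjusted differences will also be reported.

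Time point 2 alone is acceptable if fixed in advance. A mixed model for time points 3 to 5, with both covariates interacting with time and an unstructured covariance, is an alternative; it matches the separate ANCOVAs only when those three ratings are complete.

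The cost is two or three sentences of SAP text, one or two degrees of freedom per contrast, a rule for missing covariates, and the small loss of power given above if the ratings are nearly uncorrelated. No new data are needed.
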